## **3.2 Study Outcome Measures**

### **3.2.1 Primary Endpoints**

#### Safety and Reactogenicity:

1. Frequency and severity of solicited injection site and systemic reactogenicity from time of study vaccine administration through Day 8 after each administration of study vaccine overall and by dosage group and pre-vaccination flavivirus immune status.
2. Frequency and severity of unsolicited vaccine-related adverse events (AE), including vaccine-related laboratory AE, from first administration of study vaccine until 28 days after the last vaccination overall and by dosage group and pre-vaccination flavivirus immune status.
3. Frequency, type, and duration of serious adverse events (SAE) and adverse events of special interest (AESI) considered related to study vaccine from the first administration of study vaccine until the end of the study overall, and by dosage group and pre-vaccination flavivirus immune status.
4. Frequency of new onset chronic medical conditions reported at any time from the first administration of study vaccine until the end of the study overall, and by dosage group and pre-vaccination flavivirus immune status.
5. Comparison of the frequency, type, and duration of vaccine-related Grade 3 local, systemic, or laboratory AE, and Grade 2 or greater local or systemic reactogenicity through Day 8 after each study vaccine administration between dosage groups and by pre-vaccination flavivirus immune status.
6. Comparison of study withdrawals and discontinuation of study vaccination due to any reason between dosage groups and by pre-vaccination flavivirus immune status.

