### 9.2 Methods and Timing for Assessing, Recording, and Analyzing Safety Parameters

#### 9.2.1 Adverse Events

**Adverse Event (AE):** International Conference on Harmonisation (ICH) E6 defines an AE as any untoward medical occurrence in a patient or clinical investigation subject administered a pharmaceutical product regardless of its causal relationship to the study treatment. An AE can therefore be any unfavorable and unintended sign (including an abnormal laboratory finding), symptom, or disease temporally related to the use of a medicinal (investigational) product. FDA defines an AE as any untoward medical occurrence following the use of a study intervention/product in humans, whether or not considered related to study intervention.

---

The occurrence of an AE may come to the attention of study personnel during study visits and interviews of a study recipient presenting for medical care, or upon review by a study monitor.

AEs, including solicited local (injection site) and systemic (subjective and quantitative) reactions, will be captured on the appropriate case report form. Information to be collected for unsolicited AEs includes event description, date of onset, licensed study physician's assessment of severity and relationship to study vaccine or study product and alternate etiology (if not related to study vaccine) (assessed only by those with the training and authority to make a diagnosis and listed on the Form FDA 1572 as the site principal investigator or sub-investigator), date of resolution of the event, seriousness and outcome. AEs occurring during the study and reporting period will be documented appropriately regardless of relationship. AEs will be followed through resolution.

Any medical condition that is present at the time that the subject is screened will be considered as baseline and not reported as an AE. However, if the severity of any pre-existing medical condition increases, it will be recorded as an AE.

Adverse events characterized as intermittent require documentation of onset and duration of each episode. The start and stop date of each reported AE will be recorded on the appropriate case report form.

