3.2. Endpoints

Primary Endpoints:

1. Frequency and severity of solicited injection site and systemic reactogenicity from time of study vaccine administration through Day 8 after each administration of study vaccine overall and by dosage group and pre-vaccination flavivirus immune status.
2. Frequency and severity of unsolicited vaccine-related adverse events (AE), including vaccine-related laboratory AE, from first administration of study vaccine until 28 days after the last vaccination overall and by dosage group and pre-vaccination flavivirus immune status.
3. Frequency, type, and duration of serious adverse events (SAE) and adverse events of special interest (AESI) considered related to study vaccine from the first administration of study vaccine until the end of the study overall, and by dosage group and pre-vaccination flavivirus immune status.
4. Frequency of new onset chronic medical conditions reported at any time from the first administration of study vaccine until the end of the study overall, and by dosage group and pre-vaccination flavivirus immune status.
5. Comparison of the frequency, type and duration of vaccine-related Grade 3 local, systemic, or laboratory AE, and Grade 2 or greater local or systemic reactogenicity through Day 8 after each

study vaccine administration between dosage groups and by pre-vaccination flavivirus immune status.

6. Comparison of study withdrawals and discontinuation of study vaccination due to any reason between dosage groups and by pre-vaccination flavivirus immune status.

Secondary Endpoints:

1. Frequency of seroconversion to ZIKV at each post-vaccination visit measured by ZIKV ELISA and neutralization assay in comparison with baseline samples (collected at Visit 00) overall, and by dosage group and pre-vaccination flavivirus immune status.
2. Per Visit GMT as measured by ZIKV ELISA and neutralization assay after each study vaccine administration and for each post-vaccination visit overall, and by dosage group and pre-vaccination flavivirus immune status.
3. Peak GMT as measured by ZIKV ELISA and neutralization assay after each vaccination and overall, and by dosage group and pre-vaccination flavivirus immune status.
4. Proportion of subjects with at least a 4-fold rise in ZIKV GMT as measured by ZIKV ELISA and neutralization assay at 4 weeks after each vaccination compared with baseline overall, and by dosage group and pre-vaccination flavivirus immune status.

Exploratory Endpoints:

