9.3.1. Solicited Events and Symptoms

Statistical comparisons of the frequency and duration of vaccine related Grade 3 local, systemic, or laboratory AE, and Grade 2 or greater local or systemic reactogenicity are presented post dose 1, post dose 2, and post any dose in [Table 43](#), overall and by pre-vaccination flavivirus immune status. Frequencies of each adverse event are compared between dosage groups using Fisher’s Exact test. The distribution of the duration of adverse events (excluding laboratory AEs) will be compared between all dosage groups using the 2-samples Wilcoxon rank sum test.

The frequency and proportion of subjects experiencing any local or systemic solicited event over the 8-day post-vaccination reporting period will be summarized by dose number, pre-vaccination flavivirus immune status, severity and treatment group in [Table 44](#) (post dose 1, post dose 2, and post any dose).

The number, percentage, and exact 95% CI of subjects experiencing each solicited event over the 8-day post-vaccination reporting period, collected in-clinic pre-vaccination, post-vaccination and via memory aid, will be summarized by pre-vaccination flavivirus immune status, dose number and symptom in [Table 45](#) (all subjects), [Table 46](#) (baseline ZIKV seropositive subjects), [Table 47](#) (baseline ZIKV seronegative subjects), [Table 48](#) (baseline ZIKV seropositive and DENV seropositive subjects), [Table 49](#) (baseline ZIKV seropositive and DENV seronegative subjects), [Table 50](#) (baseline ZIKV seronegative and DENV seropositive subjects), and [Table 51](#) (baseline ZIKV seronegative and DENV seronegative subjects).

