[Implementation note: N = Number of subjects in the Safety population with specified baseline flavivirus immune status]

Table 39: Overall Summary of Adverse Events – Baseline ZIKV Seropositive and DENV Seropositive Subjects

[Implementation note: N = Number of subjects in the Safety population with specified baseline flavivirus immune status]

Table 40: Overall Summary of Adverse Events – Baseline ZIKV Seropositive and DENV Seronegative Subjects

[Implementation note: N = Number of subjects in the Safety population with specified baseline flavivirus immune status]

Table 41: Overall Summary of Adverse Events – Baseline ZIKV Seronegative and DENV Seropositive Subjects

[Implementation note: N = Number of subjects in the Safety population with specified baseline flavivirus immune status]

Table 42: Overall Summary of Adverse Events – Baseline ZIKV Seronegative and DENV Seronegative Subjects

[Implementation note: N = Number of subjects in the Safety population with specified baseline flavivirus immune status]

14.3.1.1 Solicited Adverse Events**Table 43: Comparison of the Frequency, Type and Duration of Vaccine-Related Grade 3 Local, Systemic or Laboratory AEs and Grade 2 or Greater Local or Systemic Reactogenicity Through Day 8 Post Vaccination**

Post Dose Number	AE Type	Symptom/Lab AE	2.5 mcg ZPIV		5 mcg ZPIV		Placebo		p-value		
			n	Median Duration (Days)	n	Median Duration (Days)	n	Median Duration (Days)	^a Frequency	^b Duration	
All Subjects											
Post Dose 1	Number of Subjects in the Safety Population Who Received the Specified Dose			x	N/A	x	N/A	x	N/A	N/A	
	Vaccine related Grade 3 local, systemic or laboratory AE	[Event 1]	x	x.x	x	x.x	x	x.x	x.XXX	x.XXX	
		[Event 2]							x.XXX	x.XXX	
		[Event 3]							x.XXX	x.XXX	
		Etc.							x.XXX	x.XXX	
	*Grade 2 or greater local or systemic reactogenicity	[Event 1]							x.XXX	x.XXX	
		[Event 2]							x.XXX	x.XXX	
		[Event 3]							x.XXX	x.XXX	
		Etc.							x.XXX	x.XXX	
Repeat Post Dose 1 for:											
Baseline ZIKV Seropositive											
Baseline ZIKV Seronegative											
Baseline ZIKV Seropositive and DENV Seropositive											
Baseline ZIKV Seropositive and DENV Seronegative											
Baseline ZIKV Seronegative and DENV Seropositive											
Baseline ZIKV Seronegative and DENV Seronegative											
All Subjects											
Post Dose 2	Number of Subjects in the Safety Population Who Received the Specified Dose			x	N/A	x	N/A	x	N/A	N/A	
		[Event 1]	x	x.x	x	x.x	x	x.x	x.XXX	x.XXX	

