Table 43: Comparison of the Frequency, Type and Duration of Vaccine-Related Grade 3 Local, Systemic or Laboratory AEs and Grade 2 or Greater Local or Systemic Reactogenicity Through Day 8 Post Vaccination (continued)

	Vaccine related Grade 3 local, systemic or laboratory AE	[Event 2]							X.XXX	X.XXX	
		[Event 3]							X.XXX	X.XXX	
		Etc.							X.XXX	X.XXX	
	*Grade 2 or greater local or systemic reactogenicity	[Event 1]							X.XXX	X.XXX	
		[Event 2]							X.XXX	X.XXX	
		[Event 3]							X.XXX	X.XXX	
		Etc.							X.XXX	X.XXX	
Repeat Post Dose 2 for:											
Baseline ZIKV Seropositive											
Baseline ZIKV Seronegative											
Baseline ZIKV Seropositive and DENV Seropositive											
Baseline ZIKV Seropositive and DENV Seronegative											
Baseline ZIKV Seronegative and DENV Seropositive											
Baseline ZIKV Seronegative and DENV Seronegative											
All Subjects											
	Post Any Dose	Number of Subjects in the Safety Population	x	N/A	x	N/A	x	N/A	N/A	N/A	
	Vaccine related Grade 3 local, systemic or laboratory AE	[Event 1]	x	x.x	x	x.x	x	x.x	X.XXX	X.XXX	
		[Event 2]							X.XXX	X.XXX	
		[Event 3]							X.XXX	X.XXX	
		Etc.							X.XXX	X.XXX	
	*Grade 2 or greater local or systemic reactogenicity	[Event 1]							X.XXX	X.XXX	
		[Event 2]							X.XXX	X.XXX	
		[Event 3]							X.XXX	X.XXX	
		Etc.							X.XXX	X.XXX	
Repeat Post Any Dose for:											

Table 43: Comparison of the Frequency, Type and Duration of Vaccine-Related Grade 3 Local, Systemic or Laboratory AEs and Grade 2 or Greater Local or Systemic Reactogenicity Through Day 8 Post Vaccination (continued)

Baseline ZIKV Seropositive
Baseline ZIKV Seronegative
Baseline ZIKV Seropositive and DENV Seropositive
Baseline ZIKV Seropositive and DENV Seronegative
Baseline ZIKV Seronegative and DENV Seropositive
Baseline ZIKV Seronegative and DENV Seronegative

n = Number of subjects
* Through Day 8 post vaccination
^a Frequencies of adverse events compared between ZPIV dosage groups using Fisher's Exact test.
^b Distribution of the duration of adverse events compared between ZPIV dosage groups using Wilcoxon 2-sample test.
Only the frequency, not the duration of laboratory AEs will be compared.

Table 44: Number and Percentage of Subjects Experiencing Any Local or Systemic Solicited Events through Day 8 Post Vaccination by Dose, Baseline Flavivirus Immune Status, Severity and Treatment Group

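### Primary endpoint 5 names the duration of vaccine-related Grade 3 laboratory AEs, but SAP 9.3.1 and Table 43 leave laboratory AEs out of the duration comparison without giving a reason

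*SAP*

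**What the plan says.** Endpoint 5 is worded almost identically in both documents. Protocol 3.2.1 has "Comparison of the frequency, type, and duration of vaccine-related Grade 3 local, systemic, or laboratory AE"; SAP 3.2 has "Comparison of the frequency, type and duration of vaccine-related Grade 3 local, systemic, or laboratory AE". Both add Grade 2 or greater local or systemic reactogenicity through Day 8, and both ask for the comparison between dosage groups and by baseline flavivirus status.

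SAP 9.3.1 opens by announcing "Statistical comparisons of the frequency and duration of vaccine related Grade 3 local, systemic, or laboratory AE" in Table 43. Its second sentence assigns Fisher's exact test to frequency. Its third sentence assigns a two-sample Wilcoxon rank sum test to duration: "The distribution of the duration of adverse events (excluding laboratory AEs) will be compared between all dosage groups". The Table 43 footnotes narrow this to the two vaccine doses ("Distribution of the duration of adverse events compared between ZPIV dosage groups using Wilcoxon 2-sample test") and confirm the exclusion: "Only the frequency, not the duration of laboratory AEs will be compared".

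On data collection, Protocol 9.2.1 states: "The start and stop date of each reported AE will be recorded on the appropriate case report form". Protocol 9.4 has all AEs followed to resolution or stabilisation.

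**The concern.** One paragraph of the SAP promises a comparison and then withdraws part of it, and the withdrawn part is named in a primary endpoint. A reader of the final report would find how many recipients of each dose had a related Grade 3 laboratory abnormality, but no planned comparison of how long it lasted. An abnormality that cleared by the next draw and one that persisted would count the same in the dose comparison. Section 15, where a reader would look for an explanation, covers the enrolment change after the hurricane, the merged interim analyses, the wider baseline serology and the revised second exploratory endpoint. It does not cover this.

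**Working it through.** The main check is textual.

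1. Endpoint 5 (Protocol 3.2.1, SAP 3.2): laboratory AEs named, duration named.
2. SAP 9.3.1, first sentence: laboratory AEs named, duration named.
3. SAP 9.3.1, third sentence: laboratory AEs removed from the duration test.
4. Table 43: the Grade 3 block is headed local, systemic or laboratory AE and has a median-duration column for each arm; a footnote removes laboratory AEs from the duration comparison only.
5. Protocol 11.4.2: duration is summarised for local and systemic reactions; laboratory AEs are shown by visit and toxicity grade, with no duration.
6. SAP section 15: no entry.

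Items 1 and 2 conflict with item 3 and the Table 43 footnote. Item 5 shows that the protocol's endpoint and its own analysis section also disagree.

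**Can duration be measured?** Safety laboratories are scheduled on Days 8 and 15 after each dose (SAP 4.5), which is study Days 8, 15, 36 and 43.

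- An abnormality found on Day 8 and gone on Day 15 is recorded as lasting 15 − 8 = 7 days if dated by draws. Its true length could be anything up to just under 15 − 1 = 14 days, with onset after vaccination on Day 1.
- One still present on Day 15 has no further scheduled draw for 36 − 15 = 21 days, although SAP 9.6 allows unscheduled follow-up tests.

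The dates therefore separate a brief abnormality from a persistent one, but not three days from six.

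**How many subjects?** The documents give no figure for duration. The nearest is the SAP section 5 statement of at least 80% power to see one event in a dose cohort at a true rate of 4.5%. It reproduces: 1 − (1 − 0.045)^35 = 0.8004. At that rate the expected number affected is 0.045 × 45 = 2.0 on 5 mcg and 0.045 × 35 = 1.6 on 2.5 mcg.

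For a Wilcoxon test among a and b affected subjects with untied durations, the smallest exact two-sided p is 2/C(a+b, a):

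- 2 v 2: 2/6 = 0.33
- 3 v 3: 2/20 = 0.10
- 4 v 4: 2/70 = 0.029

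The 4.5% is a detectable rate, not a forecast, so a range is needed. Assume the same event rate r in both groups, 45 v 35 recipients. The chance that both groups have at least one event is [1 − (1 − r)^45] × [1 − (1 − r)^35]. The chance that p < 0.05 is attainable at all sums the two binomial probabilities over every pair (a, b) with 2/C(a+b, a) < 0.05.

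| Assumed rate | Expected affected (5 v 2.5 mcg) | Both groups have an event | p < 0.05 attainable |
|---|---|---|---|
| 1% | 0.45 v 0.35 | 10.8% | 0.0% |
| 2% | 0.90 v 0.70 | 30.3% | 0.0% |
| 5% | 2.25 v 1.75 | 75.1% | 3.6% |
| 10% | 4.5 v 3.5 | 96.6% | 48.3% |

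For rates of 5% or less, a description is informative and a test is not.

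**The case against.** The strongest defence is that the exclusion is sensible and consistent with the protocol's analysis section. Start and stop dates for laboratory AEs largely follow the draw dates, so a rank test on them would partly compare visit schedules. Protocol 11.4.2 limits duration to local and systemic reactions, so it can be argued that no planned analysis was changed and section 15 had nothing to record. Protocol 11.1 describes the study as exploratory, without formal hypotheses.

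Persistence can also be partly seen elsewhere. Tables 201–206, 217–221 and 229–231 show related laboratory abnormalities by grade, arm and visit, and Tables 192–194 list abnormal results by subject and study day. The footnote rules out comparing laboratory durations, not displaying them, so the median-duration column of Table 43 might still be filled for laboratory rows.

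Much of this stands, and it limits the size of the point. It does not remove it. Coarse measurement is a reason to add a caveat or to state why the comparison is dropped, and the SAP does neither. The visit tables give grades at fixed days, and Tables 192–194 have no duration column. Table 190 and Listing 11 carry durations for unsolicited AEs, but Table 36 counts laboratory AEs separately, so it is unclear whether they appear there. A median that the shell might show is not a planned summary while the text and footnote point the other way.

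**Conclusion.** The point holds for the laboratory component only: SAP 9.3.1 and Table 43 omit a comparison that primary endpoint 5 and the opening of 9.3.1 both call for, with no reason given. The consequence is moderate. No other result is biased, few subjects are likely to be involved, and the trial is exploratory. The small-number figures rest on assumed event rates, equal in both doses, and on a test among affected subjects with untied durations; the textual conflict does not depend on them.

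Two stronger readings are not supported.

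- A reader might infer that the whole duration part of endpoint 5 goes unanswered. It does not: Grade 3 local and systemic AEs and Grade 2 or greater reactogenicity get a median duration by arm and a Wilcoxon p-value, after each dose and after any dose, overall and by serostatus.
- A reader might infer that the Wilcoxon test is wrong because it appears to use only subjects who had the event, and that unaffected subjects should enter with zero days. The SAP does not state who enters the test; the layout of Table 43 only suggests it. An event has a duration only if it occurs, and frequency already has Fisher's test. Zero-filling mostly repeats that test. In a simulation (2,000 runs, 45 v 35, durations of 1 plus a Poisson count), event rates of 20% v 5% with equal durations gave rejection in 50% of runs zero-filled and 42% with Fisher. With rates of 20% in both groups and mean durations of 3 v 2 days, the zero-filled test rejected in 5.3% and the test among affected subjects in 29%.

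**What to change.** In SAP 9.3.1, delete the parenthesis that removes laboratory AEs from the duration comparison, and delete the matching Table 43 footnote. State that the duration of vaccine-related Grade 3 laboratory AEs will be reported by dose group as n, median and range, from the AE start and stop dates, with any event still ongoing marked as such. Add a table note that these dates depend on the Day 8 and Day 15 sampling schedule and on any unscheduled follow-up draws. A p-value is optional, given the numbers expected.

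If the sponsor prefers to keep the exclusion, the first sentence of 9.3.1 should be reworded to match, and the departure from endpoint 5 should be recorded with its reason in section 15.

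The cost is a few words in the SAP, a change to one table shell and a little programming, with no new data. The downside is that the laboratory durations are approximate and the table must say so.

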#### 7.1.2 Physical Examination

At the screening visit (Visit 00), an abbreviated physical examination (excluding pelvic and rectal examinations) will be performed by a study clinician licensed to make medical diagnoses and listed on the Form FDA 1572 as the site principal investigator or sub-investigator. For all visits following the screening visit, a targeted physical examination may be performed by a study

---

clinician licensed to make medical diagnoses and listed on the Form FDA 1572 as the site principal investigator or sub-investigator, if indicated based on subject's interim medical history.

Vital signs (oral temperature, pulse, and blood pressure) will be collected if indicated at the time of physical examination. Subjects must not eat or drink anything hot or cold, or smoke within 10 minutes prior to taking oral temperature. Vital signs must be normal by protocol toxicity grading scale or determined to be normal-variant by investigator. In the event of an abnormal heart rate or blood pressure due to physiological variation or activity, the subject may rest for 10 minutes in a quiet room, and then blood pressure and/or heart rate may be re-measured. The repeated measurement may be used to determine eligibility per the judgment of the investigator.

Height and weight will be collected on the screening visit to determine Body Mass Index (BMI).

Pre-administration reactogenicity assessments will be performed prior to each study vaccination, then the study vaccination will be given. A subject with mild pre-administration reactogenicity that is transient, resolving, or clinically insignificant may be enrolled at the investigator's discretion.

Subjects will be observed in the clinic for at least 30 minutes after each study vaccination. The study vaccination site will be examined, post-administration reactogenicity assessments will be performed, and any AE or SAEs will be assessed and recorded on the appropriate case report form prior to discharge from the clinic.

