## **8.2 Study Enrollment and First Vaccination Visit**

### **8.2.1 Visit 01, Study Day 1, Enrollment and First Vaccination**

- Reconfirm subject's willingness to participate prior to performing any study procedures, including consent for future use of samples prior to administration of the first study vaccination.
- Perform a urine pregnancy test within 24 hours prior to study vaccine administration on all female subjects of childbearing potential. Results must be known and negative prior to enrollment and receipt of study vaccine.
- Review eligibility criteria, including results of all screening laboratory tests, prior to the first study vaccination to assure continued eligibility.
  - If the initial screening laboratory tests are more than 28 days old, these tests will need to be repeated (see [Section 7.2.1](#)). However, repeat testing for HIV, HCV, and HBV are not needed.
- Review medical history and any updates obtained by interview of subjects since the screening visit to assure continued eligibility.

- Ask about febrile/rash illness. If the subject reports history of AFI/ARI within the past 14 days, conduct a febrile/rash illness assessment and sample collection as per [Section 8.7](#).
- Review all concomitant medications and recent vaccinations (within 30 days of signing the ICF) with subjects prior to the first vaccination for accuracy and completeness. Any new medications taken since the screening visit will be recorded on the appropriate case report form and assessed for continued eligibility.
- Vital signs including oral temperature, blood pressure, and pulse, will be obtained prior to the first study vaccination.
- Perform a targeted physical examination prior to the first study vaccination, if indicated based on review of complete medical history and updates obtained by interview of subjects since the screening visit.
- Collect blood samples for, humoral immunity, HLA typing, CPT tubes and a Paxgene tube prior to vaccination.
- Enroll and randomize subjects in Advantage EDC prior to the first study vaccination.
- Perform pre-administration reactogenicity assessment prior to the first study vaccination to establish baseline. Subjects will then receive a single dose of study vaccine via IM injection into the deltoid muscle of the preferred arm. The site of injection (right or left arm) and time of administration will be recorded on the case report form.

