Baseline Flavivirus Immune Status	Severity	2.5 mcg ZPIV (N=X)		5 mcg ZPIV (N=X)		Placebo (N=X)		All Subjects (N=X)	
		n	%	n	%	n	%	n	%
Post Dose 1									
All Subjects	Number of Subjects	x	N/A	x	N/A	x	N/A	x	N/A
	None	xx	Xx	xx	xx	xx	xx	xx	xx
	Mild								
	Moderate								
	Severe								
Baseline ZIKV Seropositive	Number of Subjects								
	None								
	Mild								
	Moderate								
	Severe								
	Not Reported								
Baseline ZIKV Seronegative	Number of Subjects								
	None								
	Mild								
	Moderate								
	Severe								
	Not Reported								
Baseline ZIKV Seropositive and DENV Seropositive	Number of Subjects								
	None								
	Mild								
	Moderate								

Table 44: Number and Percentage of Subjects Experiencing Any Local or Systemic Solicited Events through Day 8 Post Vaccination by Dose, Baseline Flavivirus Immune Status, Severity and Treatment Group (continued)

	Severe								
	Not Reported								
Baseline DENV Seropositive and DENV Seronegative	Number of Subjects								
	None								
	Mild								
	Moderate								
	Severe								
	Not Reported								
Baseline DENV Seronegative and DENV Seropositive	Number of Subjects								
	None								
	Mild								
	Moderate								
	Severe								
	Not Reported								
Baseline DENV Seronegative and DENV Seronegative	Number of Subjects								
	None								
	Mild								
	Moderate								
	Severe								
	Not Reported								
Repeat for:									
Post Dose 2									
Post Any Dose									
In this table, subjects who reported not having a symptom are listed as "None", while subjects who did not complete their Memory Aid or could not remember whether they had a symptom are listed as "Not Reported".									
Severity is the maximum severity reported post dosing for each subject.									
N=Number of subjects in the Safety population who received the specified dose.									

Table 44: Number and Percentage of Subjects Experiencing Any Local or Systemic Solicited Events through Day 8 Post Vaccination by Dose, Baseline Flavivirus Immune Status, Severity and Treatment Group (continued)

n = Number of subjects reporting an event

For subjects in Group 3 receiving vaccinations in both arms, the maximum severity in either arm is summarized

Table 45: Number, Percentage and 95% Confidence Interval of Subjects Experiencing Any Grade 1 or Greater Solicited Adverse Event, by Dose, Symptom and Treatment Group – All Subjects

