Symptom		2.5 mcg ZPIV (N=X)	5 mcg ZPIV (N=X)	Placebo (N=X)	All Subjects (N=X)
Post Dose 1					
Any Local Reaction	n (%)	x (xx)	x (xx)	x (xx)	x (xx)
	95% CI	xx.x, xx.x	xx.x, xx.x	xx.x, xx.x	xx.x, xx.x
Repeat for:					
Pain					
Erythema					
Induration (mm)					
Induration					
Pruritis					
Ecchymosis					
Tenderness					
Any Systemic Reaction	n (%)	x (xx)	x (xx)	x (xx)	x (xx)
	95% CI	xx.x, xx.x	xx.x, xx.x	xx.x, xx.x	xx.x, xx.x
Repeat for:					
Feverishness					
Fatigue					
Malaise					
Myalgia					
Arthralgia					
Headache					
Nausea					
Vomiting					
Diarrhea					
Abdominal Pain					
Rash					
Fever					
Repeat for:					
Post Dose 2					
Post Any Dose					
Each event is defined as any grade 1, 2 or 3 solicited reaction within 7 days following either dose.					
N = Number of subjects in the safety population who received the specified dose; used as the denominator for percentages.					
n = Number of subjects reporting an event					

Tables with similar format:

Table 46: Number, Percentage and 95% Confidence Interval of Subjects Experiencing Any Grade 1 or Greater Solicited Adverse Event, by Dose, Symptom and Treatment Group – Baseline ZIKV Seropositive Subjects

[Implementation note: N = Number of subjects in the Safety population with the specified flavivirus immune status at baseline.]

Table 47: Number, Percentage and 95% Confidence Interval of Subjects Experiencing Any Grade 1 or Greater Solicited Adverse Event, by Dose, Symptom and Treatment Group – Baseline ZIKV Seronegative Subjects

[Implementation note: N = Number of subjects in the Safety population with the specified flavivirus immune status at baseline.]

Table 48: Number, Percentage and 95% Confidence Interval of Subjects Experiencing Any Grade 1 or Greater Solicited Adverse Event, by Dose, Symptom and Treatment Group – Baseline ZIKV Seropositive and DENV Seropositive Subjects

[Implementation note: N = Number of subjects in the Safety population with the specified flavivirus immune status at baseline.]

Table 49: Number, Percentage and 95% Confidence Interval of Subjects Experiencing Any Grade 1 or Greater Solicited Adverse Event, by Dose, Symptom and Treatment Group – Baseline ZIKV Seropositive and DENV Seronegative

[Implementation note: N = Number of subjects in the Safety population with the specified flavivirus immune status at baseline.]

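### SAP 9.3.1 names the pre-vaccination clinic assessment as a source for the post-vaccination solicited-event rates in Tables 45-51, contradicting primary endpoint 1, SAP 4.5 and the Table 45 footnote

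*SAP*

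**What the plan says.** The SAP 9.3.1 sentence for Tables 45-51 gives two instructions. The quantity is the number, percentage and exact 95% CI of "subjects experiencing each solicited event over the 8-day post-vaccination reporting period". The sources are data "collected in-clinic pre-vaccination, post-vaccination and via memory aid".

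Other places say when counting starts:

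- SAP 3.2, primary endpoint 1: "from time of study vaccine administration through Day 8 after each administration of study vaccine".
- SAP 4.5: solicited events are collected from the moment of administration up to Day 8 after each dose.
- The footnote to the Table 45 shell, whose format Tables 46-51 share: "Each event is defined as any grade 1, 2 or 3 solicited reaction within 7 days following either dose".
- The Table 44 shell: "Severity is the maximum severity reported post dosing for each subject". The shells for Tables 52-65 use a similar post-dosing rule.

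The pre-administration assessment has a stated purpose. Protocol 8.2.1 reads: "Perform pre-administration reactogenicity assessment prior to the first study vaccination to establish baseline". Protocol 8.3.1 gives the same purpose before the second dose. Protocol 7.1.2 foresees that some subjects will have findings at that point: "A subject with mild pre-administration reactogenicity that is transient, resolving, or clinically insignificant may be enrolled at the investigator's discretion".

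**The concern.** Table 45 and its subgroup versions are the main display of solicited events for primary endpoint 1. A programmer who works from the SAP text is told to include a pre-injection source. A programmer who works from the shell is told to count only what follows a dose. I found no statement of which prevails.

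The window in the sentence does not settle the matter. The reporting period runs from Day 1 to Day 8, and the pre-injection check is also made on Day 1 of that period, so a filter on study day alone would keep the pre-injection record.

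If pre-injection records were kept, a mild headache or fatigue noted before the needle would appear as Grade 1 reactogenicity. Non-specific systemic symptoms are the most exposed. Rates would rise in every arm, and the visible difference between vaccine and placebo would shrink. The study is descriptive, so these rates and intervals are the result itself.

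**Working it through.** **1. The plan's own figure.** The only design figure is the chance of seeing at least one event, 1 − (1 − p)^n (Protocol 11.2, SAP 5). For n = 35 and p = 4.5%: 1 − 0.955^35 = 80.04%. For n = 80 and p = 2.0%: 1 − 0.98^80 = 80.14%. Both reproduce, and neither is in dispute here.

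**2. The texts side by side.**

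| Place | Does a pre-injection record count? |
|---|---|
| SAP 9.3.1, sources for Tables 45-51 | Yes, read literally |
| SAP 9.3.1, window in the same sentence | No in wording; a Day 1 filter alone would not exclude it |
| SAP 3.2, primary endpoint 1 | No |
| SAP 4.5 | No |
| Table 45 footnote | No |
| Tables 44 and 52-65, severity rule | No |
| Tables 66-128, Figures 52-57 | Shown apart from the post-dose days |

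The conflict is confined to one phrase and to Tables 45-51.

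**3. Size if the phrase were followed.** Inputs:

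- Planned sizes from SAP 4.4.3: 45 subjects on 5 mcg, 35 on 2.5 mcg, and 5 + 5 = 10 on placebo.
- True post-dose rate p = 30% (assumed).
- Proportion q with a pre-dose symptom, 1% to 10% (assumed; the documents give none).

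If pre-dose and post-dose symptoms are independent, the reported rate is p + q(1 − p), and the excess is q(1 − p).

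| q | Reported rate | Extra subjects of 35 | Extra subjects of 45 |
|---|---|---|---|
| 1% | 0.30 + 0.01 × 0.70 = 30.7% | 0.245 | 0.315 |
| 3% | 0.30 + 0.03 × 0.70 = 32.1% | 0.735 | 0.945 |
| 5% | 0.30 + 0.05 × 0.70 = 33.5% | 1.225 | 1.575 |
| 10% | 0.30 + 0.10 × 0.70 = 37.0% | 2.450 | 3.150 |

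Without independence, the excess lies between 0 (everyone with a pre-dose symptom also reports a post-dose one) and q (nobody does). At q = 10% the reported rate would lie between 30% and 40%.

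**4. Effect on contrasts.** With the same q in two arms, the reported difference is [p1 + q(1 − p1)] − [p0 + q(1 − p0)] = (p1 − p0)(1 − q). It shrinks by a factor of 0.99 to 0.90. In the placebo column one subject is 1/10, or 10 percentage points.

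**5. The any-dose rows.** Two pre-dose checks apply. If they are independent, the proportion with at least one pre-dose symptom is 1 − (1 − q)²: 1.99% for q = 1% and 19.0% for q = 10%.

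**The case against.** The strongest reply is that every definition of the event is post-dose and the phrase merely describes how solicited data are gathered. Protocol 11.4.2 also limits the rate to the 7 days after vaccination. A careful programmer would follow the footnote. This reply stands as far as intent goes. A reader might infer that primary endpoint 1, as planned, counts symptoms present before the injection; the documents do not support that. They show that one sentence permits it while the other texts exclude it.

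A reader might also infer that the pre-administration assessment is never used as a baseline. That is not supported either. The protocol designates it as the baseline before each dose, and the SAP displays it separately by dose in Tables 66-128 and Figures 52-57.

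Nor is there a breach of the protocol's AE rule, "However, if the severity of any pre-existing medical condition increases, it will be recorded as an AE". That rule concerns conditions present at screening and is not a per-dose rule for passing symptoms on Day 1 or Day 29.

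The effect is bounded in grade. Only mild findings are allowed before the first dose, and Protocol 9.5.2 bars the second dose while a Grade 2 or greater event is present. Counting pre-dose findings would therefore touch the Grade 1 or greater rates and hardly the Grade 2 and Grade 3 comparisons in Table 43.

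The SAP has no rule for a symptom that begins before the dose and continues unchanged. That is a choice of derivation and not an error. Counting every solicited symptom in the window regardless of cause is defensible, and the placebo arm shows the background. Requiring an event to be new or of higher grade would drop a symptom that resolved and then returned at the same grade, which is an undesirable loss in a Phase 1 safety study.

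What the reply does not remove is the contradiction. The source list is explicit, and an intended reading is no substitute for a consistent specification.

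**Conclusion.** The source phrase in SAP 9.3.1 is wrong as written and should be corrected for Tables 45-51. It is an inconsistency of specification in a primary-endpoint display, with possible upward bias in Grade 1 or greater rates if it is programmed literally. No bias is shown to have been planned or to have occurred.

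Under the assumptions above (true rate 30%, pre-dose prevalence 1% to 10%, independence), the inflation would be 0.7 to 7.0 percentage points. It is zero if no subject has a pre-dose symptom or if the footnote is followed. Tables 44 and 52-65 do not contain the phrase and need no correction on this ground.

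**What to change.** In the SAP 9.3.1 sentence for Tables 45-51, do one of the following:

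- delete pre-vaccination from the list of sources; or
- state that the pre-administration assessment is only the baseline for that dose, is displayed in the pre-dose column of Tables 66-128 and in Figures 52-57, and does not contribute to post-dose event counts.

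The programming specification should then separate the two Day 1 records by time relative to the injection and not by study day.

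Optionally, add a sensitivity summary of events that are new, or of higher grade than in the pre-administration assessment for that dose. It should stand beside the main tables and not replace them, because of the same-grade recurrences it would omit. If it is added, the baseline must be defined per dose, since the general rule in SAP 3.3 refers only to the first vaccination.

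The required change costs one sentence and no new data. The optional summary costs one derivation flag on data already collected.
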